Patient Recruitment: The PI has the unique resource of a clinic at Thomas Jefferson University, where 60 KS boys are followed. All are untreated with any androgen. We will also recruit additional patients by notifying patient groups and physicians about the study.

PROCEDURES OF THE STUDY

I. Inclusion Criteria:

1. Karyotype diagnosis of Klinefelter's syndrome or Klinefelter's variants, including 48,XXYY and 48,XXXY
2. Chronological ages 4 to 12 years
3. No previous treatment with androgen or estrogen in past one year

II. Exclusion Criteria:

1. Major liver, kidney or other systemic disease
2. Dual diagnoses including pervasive developmental delay or autism.
3. Variant karyotypes including 46,XX males and 47,XYY males
4. A high level of mosaicism (more than 50% 46,XY cells)

III. Study Outcome:

Physical features

We will document visible phenotypic features using a digital photography system. Specific physical features examined and tests used are as follows:

1. Anthropometric measurements

1. Measurements. The clinical assessment will include measurement of height, lower segment, and arm span. Subjects' heights will be measured with a stadiometer. Measured or reported parental heights will also be recorded. Mid-parental height adjusted for the child's sex (target height) will be calculated using the formula $0.5 \times [\text{father's height (cm)} + \text{mother's height (cm)} + 13]$ (64). Target height z-scores are calculated for subjects from sex-adjusted mid-parental height obtained from the National Center for Health Statistics growth curve data (65). Arm span will be measured as the distance from right to left 3rd finger tips with patients facing the wall, with outstretched arms held parallel to the ground. Lower segment will be measured from the top of the symphysis pubis to the floor. Upper arm and lower leg circumferences will be measured. Results were converted to z-scores where possible using age- and gender-specific norms (65-67).

2. Genitalia. We will measure penile length. Standards are available for penile growth in childhood and percentiles will be recorded (68). In addition, testicular size will be assessed with the Prader orchidometer and the measured volume will be recorded.

3. Optional MRI SCAN: Patients with KS will be asked if they would have an MRI scan done at baseline and at or between the 18 and 24 month visits, when they are participating in the clinical trial.

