The KS boys will be seen at 3-6-month intervals for the two-year duration of the study. On each visit, boys will receive a careful history and physical examination to include assessment of Tanner staging (73) for pubic hair development (Tanner 1 = prepubertal-Tanner 5 = fully mature) and measurement of penile length and testicular volume. At baseline, three, and every six months thereafter, we will measure height, weight, bone age (X-ray); fasting blood work to include complete blood count, serum glucose, liver function tests (SGPT), lipid panel, thyroid studies, testosterone, and free testosterone (the active form of testosterone) levels. LH, FSH and estradiol will be measured yearly. At baseline and after one year, each boy will undergo a battery of cognitive tests that will take approximately 5 to 7 hours (see below).

The form of androgen will be the oral, nonaromatizable androgen oxandrolone. This androgen is FDA-approved for the indication of wasting and has been used safely for the past 30 years to stimulate growth in girls with Turner syndrome without virilization or major side effects. The dose, 0.06 mg/kg/day, was chosen because of the extensive previous experience with the dose of 0.06 mg/kg/day used in girls with Turner syndrome. Children will be monitored closely for signs of virilization including acne, voice changes,

development of pubic hair, and excessive bone age advancement. Since oxandrolone is nonaromatizable and cannot be converted to estradiol, we do not expect any feminizing side effects such as breast development to occur.

Safety results necessitating an approximate 10-50% reduction in medication dose or stopping the medication:

1. Bone age advancement exceeding 12 months per 6-month interval, with bone age exceeding chronologic age.
2. Signs of early pubertal development for age, including pubic hair development in boys less than 8 years of age.
3. Systolic blood pressure exceeding 95th %ile for age.
4. Diastolic blood pressure exceeding 95th %ile for age.
5. LDL cholesterol greater than 159 mg/dl.
6. HDL-C less than 20 mg/dl.
7. SGPT exceeding twice the upper limit of normal.
8. Dose can be lowered at the discretion of the investigator for other reasons such as rapid growth.

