Post-Study Visit: Per the recommendation of the Data Safety and Monitoring Board (DSMB) all study participants will be invited back for a post-study visit. This visit will occur approximately 6-28 months post-study for patients who have enrolled in the study. The post-study visit will include a history, physical examination, fasting blood work, bone age x-ray, photographs, and cognitive testing. Patients will be reimbursed \$50.00 for completion of the visit. Patients who are unable to travel to a post-study visit or who live farther than driving distance will be asked to have a blood sample drawn locally and sent to our office in Philadelphia.

ANALYSIS

The analysis will be performed in consultation with the statistician, [name] who has been collaborating with [name] for the past 15 years. The analyses described below will include 2 groups of KS boys. All results will be based on gender and age-specific standardized scores. Analysis for safety will be performed at 3, 6, 12, 18, and 24 months and an efficacy analysis for summary scores encompassing all cognitive and behavioral variables will be performed at 12 and 24 months.

I. Safety: An analysis of safety parameters will be performed for the 3, 6, 12, 18 and 24 month values based on a two-way ANCOVA, adjusting for baseline values, comparing the active treatment group versus the placebo. The safety parameters are: systolic and diastolic blood pressure, HDL, LDL cholesterol, liver function (ALT), bone age advancement, or signs of puberty (pubic hair).

II. Primary efficacy (Hypotheses 1 a,b,c): The analysis comparing androgen-treated to placebo-treated KS subjects for the one and two-year measurements will be based on the analysis of covariance (ANCOVA). We will perform a two-way ANCOVA for the five primary outcome measures at 12 and 24 months, comparing the treatment group versus the placebo, adjusting for baseline values and socioeconomic status. There will be a total of 5 summary scores. Each score will be the sum of component z-scores based on gender and age-specific normative values. The summary scores include 1. General cognition, 2. Language, 3. Working memory/executive function and attention, 4. Motor function, and 5. Self-image and behavior. The alpha level for statistical significance will be set at 0.01 for each of the five primary outcome results.

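### Pubic hair is compared between arms only by an ANCOVA pooled over all ages, which is weak for the sign the protocol singles out: pubic hair before age 8

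*Combined protocol and SAP*

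**What the plan says.** Under Procedures of the Study, section IV (Clinical trial substudy), each visit includes "assessment of Tanner staging (73) for pubic hair development (Tanner 1 = prepubertal-Tanner 5 = fully mature". The list in that section of safety results that lead to reducing or stopping medication has as item 2 "Signs of early pubertal development for age, including pubic hair development in boys less than 8 years of age".

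The between-arm comparison is in Analysis, I. Safety. It is done at 3, 6, 12, 18 and 24 months and is "based on a two-way ANCOVA, adjusting for baseline values, comparing the active treatment group versus the placebo". The parameters named are blood pressure, HDL, LDL, ALT, and then "bone age advancement, or signs of puberty (pubic hair". The second factor of the two-way model is not named. No age term, under-8 subgroup, incidence comparison, or ordinal or exact method is given for this sign.

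Two other statements bear on the point. The inclusion criterion is "Chronological ages 4 to 12 years", with two years of treatment. The opening paragraph of Analysis says "All results will be based on gender and age-specific standardized scores", but no norm or conversion for Tanner stage appears in the documents.

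**The concern.** The protocol's sign of concern is tied to age: pubic hair before 8. The planned test asks a different question, namely whether mean stage differs between arms over the whole age range after adjustment for baseline stage.

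Nearly every boy under 8 is at stage 1, and so are most boys of 9 to 11. Over two years many of the older boys will advance by one or more stages through normal puberty, and baseline stage cannot predict which. That spread enters the error term. An excess in the young boys is meanwhile averaged over everyone. A non-significant result could then be read as reassurance about virilization, a harm the protocol says it will monitor closely, when the test had little chance of showing it.

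**Working it through.** **The plan's own figure.** There is none to reproduce. The only power statement (Power Analysis) concerns working memory/executive function with 20 per group.

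**Inputs from the documents.** 120 boys in two arms; entry at 4 to 12 years; two-year treatment; Tanner stage at each visit; ANCOVA adjusted for baseline.

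**Assumptions, none stated in the documents.** 1:1 allocation, so 60 per arm; entry ages uniform on 4–12, so (8 − 4)/(12 − 4) = 50%, or 30 per arm, are under 8 at entry; natural onset at mean 11.5 years, SD 1; new pubic hair within two years in 2% of placebo boys under 8 at entry; treated rates of 20%, 30% or 40%; drug effect only in boys under 8 at entry; two-sided 0.05 (the 0.01 level is stated for the primary outcomes only).

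**Simulated power at 24 months.**

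| Analysis | 20% | 30% | 40% |
|---|---|---|---|
| All-ages ANCOVA of raw stage on arm and baseline stage | 12% | 21% | 34% |
| Same, with age as a covariate | 15% | 27% | 44% |
| ANCOVA of stage within boys under 8 at entry | 61% | 88% | 98% |
| Fisher, any new pubic hair, boys under 8 at entry | 53% | 85% | 98% |
| Fisher, same boys, only onset before age 8 | 34% | 68% | 90% |

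With no drug effect, ANCOVA rejects in about 5% of trials and Fisher in about 0.1%, so Fisher's advantage does not come from a looser error rate.

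**Hand check of the first row.** An early case moves a boy from stage 1 to 2, so the pooled mean difference is about 0.5 × (treated rate − 0.02).
- At 30%: 0.5 × 0.28 = 0.14 stage. Power of 21% corresponds to difference/SE = 1.96 − 0.81 = 1.15, so SE ≈ 0.14/1.15 = 0.12 stage.
- At 20%: 0.5 × 0.18 = 0.09; 0.09/0.12 = 0.75; power ≈ Φ(0.75 − 1.96) = 11%.
- At 40%: 0.5 × 0.38 = 0.19; 0.19/0.12 = 1.58; power ≈ Φ(1.58 − 1.96) = 35%.

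One standard error reproduces all three figures within rounding. The signal is halved by dilution and set against a standard error that comes largely from normal puberty.

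**Why the last row is lower.** Boys entering at 4–6 spend both years under 8. Those entering at 6–8 spend one year on average. The exposure that counts is (0.5 × 2 + 0.5 × 1)/2 = 75%. The last row treats the rates as two-year rates with constant hazard.

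**Sensitivity.**
- Entry ages 4 to <13, 1% placebo rate, onset SD 1.1: ANCOVA 11%, 16%, 26%; Fisher (any new pubic hair) 48%, 81%, 96%.
- On that basis, with 42 or 90 per arm: ANCOVA 9% or 13% at a 20% rate and 14% or 21% at 30%; Fisher 28% or 72%, and 60% or 95%.
- Mean onset of 11 to 12.5 years, or entry capped at 12: ANCOVA 9–14% at 20% and 15–24% at 30%.
- At a 10% rate: ANCOVA about 6%, Fisher about 8–10%, and Fisher for onset before 8 about 5%.

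**The case against.** **Age-standardised scores.** The general sentence in Analysis could mean that stage is converted to an age-specific score before the ANCOVA. If that were workable, power would be moderate: 39–49% at a 20% rate and 68–80% at 30% across the 3- to 24-month visits. Those figures require an assumed floor of 0.3 on the reference SD. The plan gives no norm for Tanner stage, the staging reference it cites (73) is titled as describing girls, and with nearly all boys under 8 at stage 1 the reference SD is close to zero. The sentence therefore does not clearly resolve the problem. It does mean that the figures for raw stage describe one reading of the plan.

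**The unnamed second factor.** It could be age group. An age main effect helps little: 12% at a 20% rate and 21% at 30%, under the wider entry-age range.

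**Earlier visits.** If the same rates were already reached by 3–12 months, when normal puberty adds less noise, the pooled test has 22–31% power at 20% and 43–60% at 30%. This softens the point but does not remove it.

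**Readings that go too far.** A reader might infer that early virilization would go unnoticed. The documents do not support that: each boy is checked at every visit against the age-8 criterion, and with 27 treated boys under 8 the chance of at least one case is 1 − 0.95^27 = 75% at a 5% rate and 1 − 0.90^27 = 94% at 10%. What is missing is a usable comparison between arms. A reader might also infer that ANCOVA on a staged sign is itself the fault. It is not: restricted to boys under 8, it does as well as Fisher's test. The loss comes from pooling ages. Nor do the documents predict rates of 20–40%; section IV reports earlier use of oxandrolone in girls with Turner syndrome without virilization.

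**Conclusion.** The point holds for the between-arm comparison. As written, and on raw stage, the pooled 24-month ANCOVA has roughly 10–35% power for treated rates of 20–40% in boys under 8. An analysis confined to those boys has roughly 50–98% for any new pubic hair, or 34–90% if onset must precede age 8. The higher range should not be read as the power for onset before 8.

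The size rests on assumed incidence, natural onset, age mix, allocation and alpha. At rates of 20% or more, the ordering held in every 24-month variation on raw stage that was tried. At 10% or below, sample size is the limit and no choice of test rescues the comparison. The effect of dose reduction after pubic hair appears was not modelled; it could narrow the difference between arms.

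**What to change.** In Analysis, I. Safety, for this sign:

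1. Report by arm the number and proportion of boys under 8 at entry who develop new pubic hair (Tanner 2 or more) on study, with an exact confidence interval and an exact test.
2. Show alongside it the number with onset before age 8, which matches item 2 of the protocol's list but has less time at risk.
3. For boys aged 8 and over at entry, compare new pubic hair with an age-stratified test.
4. Do not rely on the all-ages ANCOVA of stage for this sign, and state how, if at all, the general sentence on standardised scores applies to Tanner stage.

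The cost is a change of analysis text and a little more analysis work. Tanner stage is already assessed at each visit, so no new data are needed. The downside is low power if events are rare; the counts and intervals then show how little can be concluded.

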Klinefelter's syndrome is well suited for interventional studies because the disorder is relatively common in males, testicular failure is nearly universal, and the physical and cognitive phenotypic features have been characterized. Early androgen replacement in physiologic rather than pharmacologic dosages is a reasonable, appropriate, and safe consideration in this population. Therapeutic interventions for this relatively common disorder have not been forthcoming, and this represents a unique opportunity to replace a missing hormone and improve aspects of the cognitive and behavioral outcome. The primary specific aim of this study will test the hypothesis that androgen replacement in childhood is beneficial by comparing cognition and behavior in androgen-treated versus placebo KS groups. If successful, androgen replacement would commence early in childhood rather than adolescence or adulthood in Klinefelter's syndrome.

Specific Aim 1. Early androgen intervention, using a randomized clinical trial and treating for two years. We will evaluate five primary outcome variables: general cognition, language summary score, Working memory/executive function summary score, Motor function summary score, and Self-image and social function summary score.

Hypotheses regarding five primary outcomes:

1. Certain aspects of the KS physical, neurocognitive and behavioral phenotype will improve with childhood androgen replacement therapy.

- a. The working memory summary score will improve after two years in the androgen-treated versus the placebo group.

- b. The motor function summary score will improve after two years in the androgen-treated versus the placebo group.
- c. The self-image summary score will improve after two years in the androgen-treated versus the placebo group.

BACKGROUND AND SIGNIFICANCE

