The primary goal of this study is to test the effect of replacing the low levels of androgen in KS boys in an attempt to mimic the testosterone production that occurs normally in boys. Clinical support for androgen deficiency occurring earlier in childhood in KS boys than previously thought comes from the poor growth of the penis throughout childhood in these boys. The "standard of medical care" for initiating testosterone replacement therapy in KS males has typically been at age 11 or 12 years or older (59). Testosterone treatments in KS teenagers or adults results in appropriate virilization with increased muscle mass, more masculine body contour, increased body hair, penile growth, and amelioration of eunuchoidal tendencies.

Typically, adult replacement doses of 200 mg of testosterone esters such as testosterone enanthate or cypionate are given every two weeks and newer formulations utilizing the intradermal or oral route are also available in relatively high adult-level, replacement dosages. There are relatively few options for lower dose androgen replacement. One attractive consideration is the oral androgen oxandrolone which has been used safely in boys with delayed puberty and in girls with Turner syndrome for over twenty years and is FDA approved for children and adults for the indication of wasting (60-62). Oxandrolone safely increased muscle mass in prepubertal boys with constitutional delay of growth (63). We propose a two-year clinical trial using two doses of oxandrolone versus placebo in young KS boys, ages 4-12 years (see below).

RESEARCH DESIGN

Study Design: This study consists of a clinical trial composed of an eligible subset of KS boys ages 4-12 years. The randomized design excludes bias in the assignment of patients to the treatment group and ensures optimal matching of the treatment group, which includes: 1. Oxandrolone (0.06 mg/kg PO, daily), or 2. oral placebo. The PI, patients, and research assistant will be blinded as to whether the oral medication is oxandrolone or placebo. The randomization is performed by the research pharmacy.

Study Population: For the clinical trial, KS boys ages 4-12 years will be randomly assigned to one of two treatment groups (androgen versus no androgen). We will recruit 180 males (60 per year for 3 years) assuming an approximate 30% drop out rate, to accrue a total of 120 patients for the clinical trial substudy.

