1. Skeletal x-rays of the hands will be obtained for all subjects. Bone age will be determined according to the method of Greulich and Pyle (69).

Cognitive Outcome summary scores (To be age-appropriate):

1. General Cognition summary score (KS males, ages 2-60)
 - a. The Differential Ability Scales-(DAS)
2. Language summary score (age-appropriate):
 - Phonological
 - a. Comprehensive test of Phonological Processing (CTOPP).
 - Verbal Memory
 - a. California Verbal Learning Test-Children's Version (CVLT)
 - b. Children's Memory Scale (CMS)-story memory.
 - Expressive
 - a. Expressive one word vocabulary test
 - b. Rapid naming (NEPSY)
 - c. Test of language Competence (TLC) – Oral Expression
 - Receptive
 - a. Peabody Picture Vocabulary Test (PPVT)
 - b. Token Test
3. Working memory/Executive function/Attention summary score
 - a. Digit span backwards (DAS)

- b. Connors' Continuous Performance Test II (CPT II) and Kiddie Version (K-CPT)
- c. Connors' Rating Scales-Revised
- d. Verbal Fluencies-NEPSY(semantic)
- e. Design fluency-NEPSY

4. Motor function summary score
 - Strength
 - a. Bruininks-Oseretsky Test of Motor Proficiency
 - Fine motor
 - a. Bruininks-Oseretsky Test of Motor Proficiency (BOTMP)-Fine Motor Composite
 - Gross Motor
 - a. Bruininks-Oseretsky Test of Motor Proficiency (BOTMP)-Gross motor composite
 - b. NEPSY-praxis
5. Self-image summary score-Males less than 21 years of age
 - Social Function (Competence)
 - a. Behavior Assessment System for Children (BASC)
 - b. Child Behavior Checklist (CBCL)
 - Affect and Behavior
 - a. Revised Child's Manifest Anxiety Scale (RCMAS)

IV. Clinical trial substudy: Boys with Klinefelter's syndrome will enter the study at ages 4-12 years. At baseline, they will have a history and physical examination, cognitive and behavioral assessment, and further genetic evaluation. All potential subjects will have a full screening to determine eligibility before randomization. They will be randomized (double-blind) to one of two treatment groups: oxandrolone 0.06 mg/kg/day, or placebo control for two years. All subjects will be evaluated for safety at baseline, 3, 6, 12, 18 and 24 months, and after one and two years for end-point efficacy (cognitive and behavioral assessment).

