The oxandrolone dosage cannot be reduced by precisely 50% because of the nature of the oxandrolone tablets that come in a single strength, 2.5 mg. The 2.5 mg pill is scored and could be accurately split to the 1.25 mg dose. The 1.25 mg dose cannot be accurately split further. Thus, according the criteria listed above, we could reduce the 3.75 mg dose to 2.5 mg and the 2.5 mg dose to 1.25 mg. Dose reduction will therefore range from approximately 10-50%, depending on the weight of the child. If the dose needs to be reduced to less than 1.25 mg/day, we will change from daily to every other day dosing.

If at any visit the child's weight is greater than the 95th percentile, the 95th percentile weight in kg will be used to calculate the dose. If this dose reduction is implemented, then additional reductions would not be implemented at that visit for the other dose reduction criteria. At a single visit, if the dose of oxandrolone is reduced for one criterion, then the dosage is not reduced again for another study criterion.

Safety results necessitating stopping the study:

If at any point in the study, two or more patients develop severe liver function changes or hypertension, the study will be stopped. These changes have not occurred with oxandrolone used in a trial with 73 girls with Turner syndrome followed for up to four years and are therefore not expected.

Criteria for Subject Withdrawal from the study and adverse event reporting:

Subjects can withdraw from the study at any time for any reason. The PI may terminate a subject's participation due to severe adverse events, noncompliance with the study, or concerns about safety. Safety data will be reviewed on an ongoing (blinded) basis by the PI.

Study compliance: We will assess patient compliance by having the families fill out study cards when they administer all medications and return the cards as well as all used and

unused study materials at the time of their visit. All pills dispensed and returned will be counted and recorded. We are currently using this procedure in other ongoing studies and have found that it is effective.

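### Primary efficacy: name 24 months as the one deciding visit for all five scores and say how missing 24-month scores are handled; a repeated-measures model is a cheap but limited further gain

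*Combined protocol and SAP*

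**What the plan says.** **Tests and level.** ANALYSIS, II. Primary efficacy: "We will perform a two-way ANCOVA for the five primary outcome measures at 12 and 24 months, comparing the treatment group versus the placebo", with baseline value and socioeconomic status as covariates. The second factor of the two-way model is not named. On the level: "The alpha level for statistical significance will be set at 0.01 for each of the five primary outcome results". No family-wise level is given, and the section does not say whether a 12-month result alone would count as success.

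**Time point.** The heading of that section refers to Hypotheses 1 a, b and c. In Specific Aims, 1a reads: "The working memory summary score will improve after two years in the androgen-treated versus the placebo group". Hypotheses 1b (motor function) and 1c (self-image) use the same time point. General cognition and language are also primary outcomes, but no hypothesis dates them. The Background (Motor abilities) justifies two years of treatment by Turner syndrome data in which a motor effect was significant at 24 months and not at 12.

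**Loss.** Study Population recruits 180 boys, "assuming an approximate 30% drop out rate, to accrue a total of 120 patients for the clinical trial substudy". The withdrawal section says: "Subjects can withdraw from the study at any time for any reason". No section gives an analysis set, a rule for missing 24-month scores or a sensitivity analysis.

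**Schedule.** Section IV, Clinical trial substudy, plans evaluation "after one and two years for end-point efficacy (cognitive and behavioral assessment". Later in the same section: "At baseline and after one year, each boy will undergo a battery of cognitive tests", with no mention of a two-year battery.

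**The concern.** Five scores at two visits make ten treatment comparisons, whereas a level of 0.01 each looks like 0.05 shared over five. If a result at either visit can be claimed, the chance of at least one false positive exceeds 0.05.

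Separately, if one ANCOVA is run per visit, the 24-month comparison ignores the 12-month scores of boys who leave between the visits. That comparison is valid if loss is random or depends only on arm and baseline. If loss depends on how a boy scored at 12 months, the two-year estimate can be too small or too large.

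**Working it through.** **1. The plan's level.** 0.05/5 = 0.01, so the level fits five tests. Independent outcomes: 1 − 0.99^5 = 0.049; Bonferroni bound 5 × 0.01 = 0.05.

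**2. Family-wise error under each reading.** The correlation between the 12- and 24-month test statistics is not in the documents; I assume 0.5 to 0.8. For one score tested at both visits, p = 1 − P(|Z1| < 2.576, |Z2| < 2.576) from the bivariate normal: 0.0190 at 0.5 and 0.0166 at 0.8.

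| Reading | Formula, independent outcomes | Result | Bound |
|---|---|---|---|
| Either visit counts, all five scores | 1 − (1 − p)^5 | 0.091 to 0.080 | 0.10 |
| Either visit counts, two undated scores only | 1 − 0.99^3 × (1 − p)^2 | 0.066 to 0.062 | 0.07 |
| 24 months only | 1 − 0.99^5 | 0.049 | 0.05 |

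If outcomes correlate 0.5 (simulated), the first row becomes 0.078 to 0.068 and the last 0.042. Over a wider grid (visit correlation 0.3–0.9, outcome correlation 0–0.5) the first row runs from 0.061 to 0.094, always above 0.05.

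**3. What a model using both visits gains under random loss.** Assumed: 180 randomised 1:1, 12% lost before month 12 and 18% between the visits. Then n1 = 0.88 × 180 = 158.4 boys have a 12-month score and n2 = 0.70 × 180 = 126 have a 24-month score. With r the between-visit correlation after adjusting for baseline, the variance of completer ANCOVA divided by that of the repeated-measures estimate is about

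1 / [1 − r²(1 − n2/n1)], where 1 − n2/n1 = 0.2045.

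| Assumed correlations (baseline–12, baseline–24, 12–24) | r | Formula | Simulated | Power at 0.50 SD, alpha 0.01: ANCOVA v model |
|---|---|---|---|---|
| 0.50 / 0.45 / 0.60 | 0.48 | 1.05 | 1.045 | 69 v 72% |
| 0.60 / 0.55 / 0.75 | 0.63 | 1.09 | 1.097 | 76 v 80% |
| 0.75 / 0.70 / 0.85 | 0.69 | 1.11 | 1.109 | 90 v 93% |

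This is worth about 5–11% more boys at 24 months: 126 × 1.045 = 132 to 126 × 1.109 = 140.

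Timing matters (middle row, simulated ratio): 1.000 if all 30% leave before month 12, 1.057 for 20%/10%, and 1.138 if all leave after month 12. If the 30% is lost before randomisation and 120 are randomised with none lost, there is no gain (73.6 v 73.4%).

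**4. Bias when loss depends on the observed 12-month score.** True effect 0.50 SD, logistic slope 0.5–1.5 per SD:

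| Who leaves | Completer ANCOVA | Repeated measures |
|---|---|---|
| Alike in both arms, no effect yet at 12 months | 0.50 | 0.50 |
| Alike in both arms, effect already at 12 months | 0.49–0.46 | 0.50 |
| Low scorers, placebo only | 0.47–0.40 | 0.50 |
| Low scorers, treated only | 0.53–0.60 | 0.50 |

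The one-arm rows are illustrations; the documents do not say why boys will leave.

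**5. Where the model does not help.** Simulated with no true effect, 30% lost and score-dependent loss in one arm: if loss depends on the unseen 24-month score, the model is still biased by 0.03–0.10 SD (ANCOVA about 0.13). If boys leave before month 12 because of their unseen score, both methods are equally biased, by 0.07–0.12 SD.

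**6. Dependence on the effect size.** The Power Analysis gives no effect size. Solving its claim of over 90% power with 20 per group at two-sided 0.05 gives (1.960 + 1.282) × √(2/20) = 1.03 SD, or about 1.05 by t test. At 1.05 SD with 63 completers per arm, power is 99.9% at 0.01 and at 0.005, so the power differences in step 3 vanish.

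**The case against.** **The plan already points to two years.** The heading of the efficacy section ties it to Hypotheses 1a–c, and the Background argues for 24 months. A reader might infer that the visits are wholly unranked and that the error is 0.10. The documents do not support that: for three scores the intended time point is clear, and 0.10 is the bound under the least favourable reading. What stands is that general cognition and language are undated, and that the analysis text tests all five scores at both visits without saying which result decides.

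**There may not be ten tests.** If the unnamed second factor is visit, each score could have one overall treatment test, matching 0.01 per outcome. The text neither says nor excludes this. It would keep the error near 0.049, but an overall test is not the two-year contrast that the hypotheses state. The loss results above assume one ANCOVA per visit.

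**The model is not a full answer.** A reader might infer that a repeated-measures model settles both problems. It does not. Choosing the visit fixes alpha, and five 24-month ANCOVAs at 0.01 would do so equally well. The model helps only with loss after month 12 that is missing at random. Boys with no post-baseline score contribute nothing to it: 0.12 × 180, about 22 boys in the assumed case.

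**The loss may precede randomisation.** Study Population can be read as 180 recruited to give 120 in the trial, and section IV says: "All potential subjects will have a full screening to determine eligibility before randomization". On that reading, if few are lost afterwards, the gain disappears. The documents do not settle it, and the absence of any missing-score rule stands either way.

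**Conclusion.** The point holds as a cheap improvement, not as an error that invalidates the trial. The efficacy section should name one deciding visit and a method for missing 24-month scores, and it does neither. The excess family-wise error is modest: about 0.068–0.091 if either visit counts for all five scores and 0.062–0.066 if only for the two undated ones, against 0.042–0.049 with 24 months alone. These figures rest on assumed visit correlations of 0.5–0.8 and, for the middle range, independent outcomes.

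The gain from the model is conditional: 5–11% more boys under the assumed timing of loss, nothing if loss precedes randomisation or month 12, and no power difference at the effect the Power Analysis implies. A reader might also infer that the planned analysis will be biased. The documents do not show this: they give no reason for or timing of loss, and ANCOVA is unbiased when loss is alike in both arms with no effect yet at 12 months.

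**What to change.** 1. **First reconcile the schedule.** Section IV and the ANALYSIS section place efficacy assessment at one and two years, while the battery sentence in section IV lists only baseline and one year. The primary contrast needs 24-month scores.
2. **Name the visit.** Make treatment at 24 months the only primary contrast for each of the five scores at 0.01, with 12 months secondary. State what the second factor of the two-way model is. This step alone fixes alpha. Splitting alpha over ten tests (0.005 each) would also control it, but at an assumed 0.50 SD (middle correlation set) it cuts 24-month ANCOVA power from 76% to 68%.
3. **Estimate that contrast with a mixed model for repeated measures**, by assigned arm: treatment, visit, treatment × visit, baseline × visit and socioeconomic status, with unstructured within-boy covariance. Include every randomised boy with at least one post-baseline score, and report by arm those with none.
4. **Add a delta-adjusted sensitivity analysis** for loss that depends on unseen scores. With 30% of treated boys lost, each 0.1 SD by which their unseen scores are worse moves the estimate by 0.30 × 0.1 = 0.03 SD.
5. **Say whether the 30% loss is before or after randomisation.**

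Cost: wording and slightly more analysis work; no extra visit or test if the two-year battery stands, and SAS is already the named software. Downsides: a benefit seen only at 12 months would no longer be primary, and the model relies on missing-at-random. Make the change in a dated amendment before any comparison of arms. The documents do not say whether one has been made; if so, label the change as later.
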